5.1.4 Safety Assessment

To characterize all systemic opioid weaning-related, device-related, IT drug-related, and procedure-related adverse events (AEs), all serious adverse events (SAEs) (regardless of relatedness), and device deficiencies (DD) for all subjects from enrollment until the subject exits.

6. Study Design

This is a prospective, multi-center, post market study with commercially available products to evaluate the pain control and opioid-related side effects following a route of delivery change from systemic opioid therapy to IT morphine therapy in subjects with chronic, intractable, non-malignant primary back pain with or without leg pain. The study will be conducted at approximately 15 study sites in the United States.

Patients that meet all inclusion criteria, do not meet any exclusion criteria, and provide written Informed Consent Form (ICF)/Health Insurance Portability and Accountability Act (HIPAA) Authorization Form will be enrolled in the study. Medtronic products used in this study will be used within the specifications of product labeling. The pharmacological agent used in the study is limited to PFMS and preservative free 0.9% Sodium Chloride Injections, USP (for dilution).

Ninety-three subjects have been enrolled into the study with the intent to achieve approximately 67 implanted subjects and at least 50 evaluable subjects at the 6-Month Visit. All subjects implanted with the IDDS will be followed through their required study exit visit. The study sample size accounts for the expected attrition anticipated throughout the duration of the study, and therefore, subjects who are exited or discontinue will not be replaced.

[figure not shown]
If an activated site does not enroll any subject within three months of activation, Medtronic may choose to terminate their participation in the study and move forward with another potential study site to ensure sufficient subject enrollments.

To ensure a distribution of data and minimize center bias in study results for analysis of the primary and secondary objectives, the maximum number of subjects that may be enrolled at a single site is 15, with Medtronic pre-approval required for additional enrollments.

Selection of subjects, treatment of subjects, and evaluation of study data are potential sources of bias. Potential sources of bias that may be encountered in this study have been considered and minimized by careful study design. Methods incorporated in the study design to minimize potential bias include (but are not limited to) the following:

- Subjects will be screened to confirm eligibility for enrollment with defined inclusion/exclusion criteria
- Subject demographics will be collected to assess possible characteristics that may influence endpoints
- To ensure widespread distribution and data among centers, the maximum number of subjects that may be enrolled at a single site is 15, with Medtronic pre-approval required for additional enrollments. Additionally, centers will each be encouraged to enroll at least 5 subjects
- A statistical analysis plan will be developed prior to analyzing data which will document pre-specified analysis and analysis methods
- All study site personnel and Medtronic personnel will be trained on their respective aspects of the study using standardized training materials
- All study site personnel will be trained on and required to follow the Clinical Investigation Plan (CIP)
- A Clinical Events Committee (CEC) will be utilized to adjudicate the relatedness and seriousness classifications of all reportable AEs and deaths

Figure 1: Embrace TDD Study Visit Flowchart

6.1 Duration

Enrollment is defined as the date the subject first signs the study informed consent/HIPAA form. Enrolled subjects will be required to attend a minimum of 7 in-office visits. Study completion for each subject is defined as the conclusion of the 6-Month Visit (Study Exit). Each subject's participation in the study is expected to last approximately 11 months from the date of enrollment to completion of the 6-Month Visit.

The duration of time needed to enroll 93 subjects in the study was 2 years and 1 month. The overall study duration, from first subject enrollment to last subject visit, is expected to last approximately 3 years. Study completion is defined as the approval of the Final Study Report and closure of all study sites.

6.2 Rationale

Information from available literature (Section 4.1) supports the need for clinical studies to assess IT morphine as an alternative route of delivery and its impact on efficacy and safety outcomes. Many chronic pain patients may not be achieving adequate pain management with systemic agents, are at higher risk for dose-limiting side effects or can become tolerant to opioids over time. Additionally, by changing the route of delivery, there is potential to eliminate the need for adjunctive chronic systemic opioids, which may lead to a reduction of opioid-related systemic side effects.

Studies of systemic opioids indicate an increase in overdose risk as a function of increased daily dose. Dunn et al. reported that adults who started use of opioid analgesics for a pain condition and were receiving 100 mg per day or more of an average prescribed daily opioid dose had an 8.9-fold increase in overdose risk compared with subjects receiving 1 to 20 mg/day of these medications. Furthermore, subjects receiving 50 to 99 mg/day had a 3.7-fold increase in overdose risk compared with subjects in the lowest-dose group.²⁴

A demonstration of overall benefit is required to justify a route of delivery change when a more invasive therapy is proposed. A combined endpoint of clinical success was chosen for this study to assess the overall benefit of the therapy. Clinical success for this study is the improvement in either pain or opioid-related side effects, at the individual subject level. Smith et al³ reported the use of a combination endpoint with malignant pain subjects, with clinical success defined as a ≥20% reduction in VAS, or equal pain scores with ≥20% reduction in opioid-related side effects.

This study is designed to establish medical evidence that intrathecal morphine is an effective alternative for the management of chronic intractable pain and implementing an opioid wean and holiday results in positive outcomes.

7. Product Description

7.1 General

The Medtronic SynchroMed II infusion system and related components and accessories used in this study are commercially available. SynchroMed II infusion system components that are commercially available after commencement of this study may also be used in addition to, or in lieu of the currently available components.

The Medtronic SynchroMed II infusion system will be the only implantable system allowed in this study and will be used in accordance with the product labeling.

The pharmacological agent used in the study is limited to PFMS and preservative free 0.9% Sodium Chloride Injections, USP (for dilution).

Table 1: Study Products

	Medtronic Product	Model
Implantable Components	Pump	8637-20 SynchroMed™ II Pump 8637-40 SynchroMed™ II Pump
	Catheters	8780 Ascenda™ Intrathecal Catheter Kit 8781 Ascenda™ Intrathecal Catheter Kit 8782 Ascenda™ Intrathecal Catheter Spinal Segment Revision Kit 8784 Ascenda™ Intrathecal Catheter Pump Segment Revision Kit
	Catheter Accessory Kits	8785 Catheter Accessory Kit 8786 Needle Catheter, Short 8787 Needle Catheter, Long 8591-38 Catheter Passer 8591-60 Catheter Passer
	Refill Kit and Catheter Access Port Kit	8540 Catheter Access Port Kit 8551 Refill Kit 8555 Refill Kit
	Clinician Devices	CT900 Clinician Programmer (tablet) A810 SynchroMed II Clinician Programmer Application A901 Communicator Manager Application A902 Patient Data Service Application 8880T2 Communicator
	Patient Devices/Accessories	TH90T01 Personal Therapy Manager (myPTM™) TM90 Communicator HH90 Handset with A820 myPTM Application software

SynchroMed II infusion system Manuals are provided with the products and are also available electronically at <http://manuals.medtronic.com/manuals/main/region>.

7.2 Dosage Form and Route of Administration

Sites will utilize PFMS per the investigator's standard of care and in accordance with the IT PFMS dosing goals and IT PFMS dose adjustment parameters outlined in Section 10.13.

Preservative-free (0.9%) Sodium Chloride Injection for IT administration: may be used to dilute PFMS to the desired concentration or to fill the pump reservoir prior to introduction of PFMS or if PFMS is removed and no other drug is placed in the pump.

7.3 Manufacturer

The SynchroMed II infusion system is manufactured by Medtronic, Inc. with operational headquarters in Minneapolis, Minnesota 55432-5604, USA.

7.4 Packaging

All Medtronic devices that will be used in this study are commercially available for IT drug delivery as an aid in the management of chronic, intractable pain. The devices specified in Section 7.1 will be shipped in their commercially available form, which includes packaging and labeling. Only commercial device products with commercial labeling will be used in this study. Each study site will order devices through their standard ordering processes and should follow their own accountability and storage processes, in accordance with the product labeling and their institution's policies and procedures.

The pharmacological agent used in this study will be PFMS. Each study site will order drug through their standard ordering processes and should follow their own accountability and storage processes, in accordance with the product labeling and their institution's policies and procedures, since these are controlled substances. No additional product accountability logs will be required for tracking these commercially available products in this study. All Medtronic device product manuals can be found electronically at <http://manuals.medtronic.com/manuals/main/region>.

7.5 Intended Population

The SynchroMed II infusion system is utilized in this study to deliver PFMS intrathecally in the treatment of patients with chronic, intractable, non-malignant, primary back pain with or without leg pain who are experiencing inadequate pain relief and/or intolerable side effects with their systemic opioid therapy.

7.6 Product Use

The Medtronic SynchroMed II infusion system and related components and accessories are commercially available in the United States and shall be used in accordance with commercial labeling. Exposure to the Medtronic study product is considered to occur from the time the subject is first exposed to the IDDS (during the device implant visit) until either the IDDS is explanted or the subject discontinues from the study.

7.7 Product Training Materials

Only investigators who are trained and experienced in implanting the SynchroMed II infusion system will perform the pump trial, pump implant, and pump refill procedures required for this clinical study. All study site personnel participating in the study will be required to complete all study-specific training as required in the Study Training Plan and have proper delegation by the Principal Investigator (PI) on the Delegation of Authority Log maintained at the site.

7.8 Product Receipt and Tracking

This is a post-market study and the Medtronic SynchroMed II infusion system and PFMS used in this study are commercially available. As this is a post-market study, study center personnel will order devices through their standard procedure for acquiring commercial product and site personnel should follow their standard procedures for tracking and managing supplies.

7.9 Product Storage

Sites should ensure proper storage conditions and record keeping for all products used in the study, per applicable labeling and per their institutions' policies and procedures.

7.10 Product Return

To fully evaluate product performance, Medtronic requests that explanted Medtronic products be returned for complete analysis. Therefore, Medtronic implantable products, explanted or opened, must be returned to Medtronic for analysis when permissible by local laws and regulations, when those products are no longer in use, regardless of reason for explants or removal from use. Furthermore, Medtronic requests the return of explanted product from non-clinical sources, such as funeral homes, and will assume responsibility for storage and disposal of the product once received.

Mailer kits with prepaid US postage are available for use within the United States to send explanted devices to Medtronic Neuromodulation Returned Product Analysis Lab. These mailers are sized to accommodate the devices from a single subject and are designed to meet postal regulations for mailing biohazardous materials.

Please contact your local Medtronic representative to obtain a Returned Product Mailer Kit or to obtain instructions on returning products to Medtronic.

All drugs utilized in this study must be disposed of as required by local laws and each site's institutional policies and procedures.

Returned Product Analysis

Devices that are returned to Medtronic, Inc. are analyzed via a Returned Product Analysis (RPA) system following specific protocols to identify root cause for failure or deficiency. When programming data are available on the IDDS, an expected longevity can be determined, and battery depletion (where applicable) can be identified as normal or premature. Upon PI request, a summary report of Medtronic's findings will be provided to the PI after analysis completion.

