7.11 Product Accountability

Product accountability is not required since the Medtronic SynchroMed II infusion system and PFMS used in this study are commercially available. All devices and drugs used during the study will be purchased by sites through their standard procedure for acquiring commercial product and maintained per the applicable product labeling and the institutions' standard procedures.

8. Study Site Requirements

All investigator and site selection activities were complete prior to implementation of CIP V3.0.

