12.6 Subject Death

The investigator must notify Medtronic immediately and the IRB (as required), after learning of a subject's death (regardless of relatedness). The death should be reported to Medtronic on the event eCRF as soon as possible. The investigator should also attempt to determine, as conclusively as possible, whether such deaths are related to the systemic opioid weaning, device, IT drug, or procedure.

If it is determined that the cause of death was related to systemic opioid weaning, device, IT drug, or procedure:

- A copy of an autopsy report should be provided to Medtronic, if an autopsy is performed
- Medtronic requests that all device system components that were being used at the time of the death be returned to Medtronic for analysis per Section 7.11
- Requested death certificates and/or source documentation if obtained, should be redacted and sent to Medtronic

If the death occurs at a location remote from the study site, it is the study site's responsibility to make three attempts to retrieve all pertinent information related to the subject's death and submit the investigator's death summary of the known events surrounding the death to Medtronic.

13. Data Review Committees

This study will utilize a Clinical Events Committee (CEC) to adjudicate the relatedness and seriousness classifications of all reportable adverse events.

The CEC may request clarification and/or additional information from the PI who reported the event. If the conclusion of the review differs from the PI's assessment, both opinions will be reported back to the investigator and noted in the final study report. Incidence rates will be tabulated using the final CEC determination.

The CEC will be external to Medtronic and independent of the study investigators. The members will have specialties appropriate to the therapeutic area and meet requirements established in the CEC charter.

14. Statistical Design and Methods

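### CIP 12.6 requests the autopsy report, death records and device components only once a death has been found related, so for a non-remote death judged unrelated nothing routinely brings that evidence to the CEC

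*Protocol*

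**What the plan says.** **CIP 12.6 (Subject Death).** The investigator must notify the sponsor immediately "after learning of a subject's death (regardless of relatedness"). The section continues: "The investigator should also attempt to determine, as conclusively as possible, whether such deaths are related" to weaning, device, IT drug or procedure. Three requests follow, all under one condition: "If it is determined that the cause of death was related to systemic opioid weaning, device, IT drug, or procedure". They are:

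- the autopsy report ("A copy of an autopsy report should be provided to Medtronic, if an autopsy is performed");
- the device components in use at death, which are to "be returned to Medtronic for analysis per Section 7.11";
- redacted death certificates or source documents, where obtained.

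A separate paragraph covers deaths that occur away from the study site. The site must try three times to gather the relevant information and must submit a death summary. That paragraph has no relatedness condition.

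**CIP 7.10 (Product Return).** Explanted or opened implantable product must be returned, where law permits, "when those products are no longer in use, regardless of reason for explants or removal from use". The section also asks for explanted product from funeral homes.

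**CIP 7.11 (Product Accountability).** "Product accountability is not required since the Medtronic SynchroMed II infusion system and PFMS used in this study are commercially available". It contains no return procedure.

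**CEC.** The bias-control list in CIP Section 6 has the CEC "adjudicate the relatedness and seriousness classifications of all reportable AEs and deaths". CIP Section 13 bases incidence rates on the CEC's final determination, and SAP 7.10 uses CEC-adjudicated relatedness in the summary tables.

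**The concern.** The autopsy report, the cause of death on the certificate and an analysis of the pump are among the things that help to decide whether a death was related. Section 12.6 asks for them only after that decision has gone one way. If the decision is that the death was related, the file grows and the finding can be confirmed or overturned. If the decision is that it was unrelated, the section prompts no further collection, and a mistaken label is less likely to be found.

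This matters here because CIP 11.1 lists component failure leading to overdose among the system complications, and states that such complications might end in death. What is at stake is the attribution of individual deaths in the safety summary. The efficacy analyses are not affected.

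**Working it through.** The plan states no figure on this point. The check is a comparison of the relevant sections.

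**1. What triggers each request after a death**

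| Item | CIP 12.6 | Elsewhere in the CIP |
|---|---|---|
| Notification | Every death | – |
| Relatedness assessment | Every death | CEC adjudication (Sections 6, 13) |
| Autopsy report | Only if found related | Counts as source documentation (16.4), but with no duty to obtain it |
| Death certificate, source documents | Only if found related | General source-access rules (16.4) |
| Device already explanted | Only if found related | Return required whatever the reason (7.10) |
| Device left in the body | Requested only if found related | Not covered by 7.10 |
| General information, remote death | Three attempts plus a summary, unconditional | – |
| General information, non-remote death | No equivalent paragraph | – |

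**2. Order of events in 12.6.** Notification comes first, then the relatedness attempt, then the three requests if the result is that the death was related. The passive wording of the condition does not name who decides. The preceding sentence is about the investigator, so the investigator's judgement is the natural reading, but that is an inference.

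**3. 12.6 against 7.10 on devices.** Section 7.10 turns on whether the product has been explanted or opened. Section 12.6 turns on whether the death was related. A pump explanted after a death judged unrelated falls under 7.10 but outside the request in 12.6. Because 12.6 cites 7.11, a site that follows the reference reaches the accountability waiver and not the wider return rule.

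**4. How the evidence reaches the CEC.** Section 13 lets the CEC ask the PI for more on any event, at its discretion. Section 7.10 sends a summary of returned-product findings to the PI on request. No section states that autopsy, certificate or device findings go to the CEC as a matter of course. The CEC charter, which could say so, is not among the documents.

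**5. What remains.** For a death that is not remote and is judged unrelated, no routine provision collects the autopsy report or certificate for the CEC. The one routine provision for the device is 7.10, and it applies only if the pump has been explanted.

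**6. Size.** The documents give no number of deaths, so no effect can be calculated. Purely to show scale, suppose one death were reclassified from unrelated to related, with none related before. Exact (Clopper-Pearson) 95% intervals are:

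- Weaning-related death, all enrolled subjects (n = 93, the SAP safety set): 0/93 = 0% (0 to 3.9%) becomes 1/93 = 1.1% (0.0 to 5.8%).
- Device-related death, implanted subjects at the CIP's intended number (n = 67): 0/67 = 0% (0 to 5.4%) becomes 1/67 = 1.5% (0.0 to 8.0%).
- The same with the assumed 33% attrition applied to actual enrolment (93 × 0.67 ≈ 62): 0/62 = 0% (0 to 5.8%) becomes 1/62 = 1.6% (0.0 to 8.7%).

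The reclassified death is hypothetical, and these are not estimates.

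**The case against.** The best answer is that the plan has other safeguards and that the two sections can be read together. Section 7.10 governs explanted product, 12.6 adds a specific request for components in use at a related death, and nothing in 12.6 says that other devices may be kept. The CEC can query any event. Remote deaths trigger unconditional retrieval. Monitors have direct access to source documents that support the eCRF, and 16.4 names autopsy reports among source documents. Pump interrogation and programming data are uploaded during the study (CIP 10.19) and kept (16.3), so some evidence on over-infusion exists without the pump. The safety summary is descriptive, in a post-market study.

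Much of this stands, and it rules out stronger readings that a reader might infer:

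- **That the pump is requested only after a related finding.** This is not so. Section 7.10 applies on its own to any explanted pump, whatever the cause of death. Neither section requires a pump to be explanted after death.
- **That the CEC adjudicates deaths labelled unrelated without the evidence.** The documents do not show this. The CEC may ask for it, and its charter is not available. What they show is that the routine provision is missing.
- **That a later query could never repair the gap.** A pump that has been buried or cremated is lost. An autopsy report or certificate that exists can still be requested later.

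The safeguards do not close the gap. CEC queries are discretionary and come after the first judgement. The retrieval duty is limited to remote deaths and does not mention the device. Access to source documents does not oblige a site to obtain a record it does not hold.

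**Conclusion.** The point holds as a defect in CIP 12.6; Section 7.10 is sound as written. The section makes routine requests for evidence on relatedness depend on a prior finding of relatedness, is narrower than 7.10 on device return, and cites the wrong section. For non-remote deaths judged unrelated, supply of this evidence to the CEC rests on ad hoc queries, while the CEC's decision determines how the death is tabulated. Any resulting error would tend towards too few related deaths.

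The size is unknown because no death count is given. If there are no deaths, nothing changes. If there are a few, the attribution of each matters to a safety summary of this size. The conclusion assumes that the relatedness finding in 12.6 comes before CEC adjudication, and that no charter provision outside these documents already supplies the evidence. The wrong cross-reference alone would be clerical. The relatedness condition is what justifies an amendment.

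**What to change.** In CIP 12.6:

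1. Remove the relatedness condition, so that for every subject death the site is asked for the autopsy report if one was performed, the death certificate and source documents if obtained, and any explanted device under 7.10 where law permits.
2. Change the reference from 7.11 to 7.10, so that the two sections give one instruction on device return.
3. State that the items available are given to the CEC before its final determination.

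Do not require post-mortem explant. Neither section requires it now, and the return mailers would not cover what it involves.

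The cost is a wording amendment and a few more record requests. Prepaid mailers and the funeral-home request already exist in 7.10. No analysis in the SAP needs to change.
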